**Statistical methods:**

Treatment effect of the primary endpoint of change from baseline in WOMAC pain sub-score will be based on a repeated measures ANOVA model including the baseline value, the treatment group, the visit, and treatment by visit as interaction. Comparison of AMZ001 gel versus placebo will be performed within the context of this model. The difference and the corresponding 95% confidence interval (CI) and p-value will be presented. The same ANOVA model used for the primary endpoint will be used to assess the treatment effect of the secondary endpoints. The significance level will be set at 5 % two-sided, and p-values will not be adjusted for multiple comparisons.

The power is determined from expected changes in the primary endpoint of the change from baseline in pain as evaluated by the WOMAC pain sub-score. The power calculation is based on data from a 4-week double-blind diclofenac sodium 2 % topical solution treatment study in knee osteoarthritis patients (Wadsworth et al. 2016). In this study using the WOMAC LK 3.1 scale (0-4 for each question), a decrease from baseline in WOMAC pain sub-score (5 questions)

Protocol ID  
AMZ001-006  
Version 1.2

22NOV2018

---

was recorded in the diclofenac treatment group of 4.5 (SD 4.5) and in the placebo group 3.6 (SD 4.2).

The estimated common SD of 4.4 in the LK 3.1 scale can be converted to a SD of  $4.4 * 2.5 = 11$  in the NRS scale. With the assumptions of the SD of 11 (NRS scale), 120 subjects enrolled in each of the double-blinded treatment arms, 10 % dropout rate, normal distribution, 5 % level of significance two-sided, 80 % power, the study will be powered to detect a treatment difference in WOMAC pain sub-score between AMZ001 BID and placebo of 4.2 on the NRS scale.

Protocol ID  
 AMZ001-006  
 Version 1.2

22NOV2018

Table 2: Schedule of Trial Procedures

Activity/Assessment	Screening 1a 	Screening 1b 	Baseline V2	On Treatment Visits				14-Day Safety Follow-up  V7
				V3	V4	V5	V6	
Study Week	-	-	0	1	2	3	4	6
Study Day	-21 to -5	-13 to -1	1	8	15	22	29	43
Visit Window (days)	-	-	0	+/- 2	+/- 2	+/- 2	+/- 2	+/- 5
Informed Consent	X							
Medical history	X							
Inclusion/exclusion criteria	X	X	X					
Demographic data	X							
Physical examination	X						X	
Skin Tolerability Assessment			X 	X	X	X	X	
Knee X-ray (both knees)	X							
Instructions on reporting pain 	X							

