### 2.2 Determination of sample size

The power is determined from expected changes in the primary endpoint of the change from baseline in pain as evaluated by the WOMAC pain sub-score. The power calculation is based on data from a 4-week double-blind diclofenac sodium 2 % topical solution treatment study in knee osteoarthritis patients (Wadsworth et al. 2016). In this study using the WOMAC LK (Likert) 3.1 scale (0-4 for each question), a decrease from baseline in WOMAC pain sub-score (5 questions) was recorded in the diclofenac treatment group of 4.5 (SD 4.5) and in the placebo group 3.6 (SD 4.2).

The estimated common SD of 4.4 in the LK 3.1 scale can be converted to a SD of 4.4 \* 2.5 = 11 in the NRS scale. Calculations based on a series of assumptions are shown below in Table **2**. With the assumptions of the SD of 11 (NRS scale), 120 subjects enrolled in each of the double-blinded treatment arms, 10 % dropout rate, normal distribution, 5 % level of significance two-sided, 80 % power, the study will be powered to detect a treatment difference in WOMAC pain sub-score between AMZ001 BID and placebo of 4.2 on the NRS scale.

WOMAC pain-subscore difference	Common SD	Power
3.8	9	0.87
	11	0.72
	13	0.57
4.0	9	0.90
	11	0.76
	13	0.61
4.2	9	0.93
	11	0.80
	13	0.66

Table 2 Power calculations for pairwise difference in WOMAC pain sub-score between AMZ001 andplacebo with 108 evaluable subjects per group, 5 % level of significance, two-sided.

The power is not adjusted for multiple comparisons and adjustment for multiplicity will not be made as there is one test only performed for the primary endpoint.

It should be noted that the current trial is not designed or powered to evaluate superiority of AMZ001 compared to Voltaren® gel, but the trial will provide important information on onset and duration of action of AMZ001 to guide future, larger trials. Also, the trial is not powered to evaluate superiority of AMZ001 applied twice daily as compared to once daily, but the trial will provide information on efficacy, safety, and tolerability of twice daily administration as compared to once daily administration.

Furthermore, the trial will be used to finalize the psychometric validation of the Pain Diary and the Satisfaction Questionnaire.

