### 4.2.1.1 Derivation of primary endpoint

The primary endpoint is the change from baseline at week 4 in the WOMAC pain sub-score in the target knee.

The WOMAC pain sub-score is derived from WOMAC Osteoarthritis Index questionnaire as the sum of questions 1 to 5. It takes values in the range 0-50, where higher values indicate greater pain. For convenience and ease of interpretation, all WOMAC scores (including the pain sub-score) will be normalised to a 0-100-point scale for data analysis.

For the primary endpoint,

normalised WOMAC pain sub-score = (WOMAC pain sub-score/50) \* 100

The full WOMAC questionnaire is assessed for the target knee at baseline (Visit 2), week 1 (Visit 3) week 2 (Visit 4), week 3 (Visit 5) and week 4 (Visit 6).

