### 4.2.1.2 Summary presentations and method of analysis

The absolute values and the absolute change from baseline in the WOMAC pain sub-score will be summarized over time by treatment group.

The primary analysis will use a restricted maximum likelihood based repeated measures mixed model (MMRM) on the dependent variable absolute change from baseline of the WOMAC pain sub-score. The analysis will include covariates of baseline value (WOMAC pain sub-score), treatment, timepoint, sex, country, the subject characteristic of unilateral/bilateral knee OA at baseline (defined by whether one or both knees meet the requirements for target knee selection) and treatment-by-timepoint interaction. An AR(1) covariance structure will be used to model the correlations between within-subject repeated measurements. The Kenward-Roger approximation will be used to estimate denominator degrees of freedom and adjust standard errors.

Sample SAS code to be used for the MMRM analysis:

```
proc mixed data=;
class treatment visit sex status subject;
model response = treatment visit treatment*visit sex country status baseline / ddfm=kr s;
repeated visit / subject=subject type=ar1;
lsmeans visit*treatment / diffs cl obsmargins;
```

run;

where *response* is the change from baseline in WOMAC pain sub-score and *baseline* is the WOMAC pain sub-score at baseline, *status* is the categorical variable of either unilateral or bilateral knee OA at baseline and *visit* is the study timepoint.

Least square mean estimates of change from baseline in WOMAC pain sub-score along with 95% confidence intervals (CI) will be presented at each time-point for each treatment group.

Estimated treatment differences at week 4 between all treatment groups along with associated 95% confidence intervals and p-values will be presented. P-values will be interpreted according to the hierarchical step-down testing procedure specified for the primary objective and also with consideration as to whether they are secondary or exploratory objectives. Model-estimated least square means and associated 95% CI of change from baseline in WOMAC pain sub-score will be plotted over time by treatment group.

The primary efficacy analysis will be based on the mITT. The robustness of the results of the primary analysis will be investigated by a sensitivity analysis based on the PP.

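### The primary MMRM holds the baseline slope equal at weeks 1 to 4; a baseline-by-visit term would be a near-costless, minor gain in precision at week 4.

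*SAP*

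**What the plan says.** The prose and the sample code in SAP 4.2.1.2 agree. The prose lists "The analysis will include covariates of baseline value (WOMAC pain sub-score), treatment, timepoint, sex, country, the subject characteristic of unilateral/bilateral knee OA at baseline", followed by a treatment-by-timepoint interaction. The code reads "model response = treatment visit treatment*visit sex country status baseline / ddfm=kr s". Neither has a baseline-by-visit term. The protocol synopsis (Statistical methods) describes a "repeated measures ANOVA model including the baseline value, the treatment group, the visit, and treatment by visit as interaction", also without one.

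The response is change from baseline. SAP 4.2.1.1 gives four post-baseline assessments of WOMAC pain, at weeks 1, 2, 3 and 4. On the covariance, SAP 4.2.1.2 says: "An AR(1) covariance structure will be used to model the correlations between within-subject repeated measurements". The contrast of interest is at the last visit: "Estimated treatment differences at week 4 between all treatment groups along with associated 95% confidence intervals and p-values will be presented".

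SAP 4.2.1.2 closes by allowing further robustness work on time and covariates. That work is discretionary and no such term is named. SAP 4.2.2.2 and 4.2.3.2 carry the same model to the other continuous endpoints.

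**The concern.** The model lets the treatment effect differ by visit but requires the regression of change on baseline to be the same at every visit. For a change score, the slope at week t is cov(Y_t, X)/var(X) - 1, where X is baseline and Y_t the score at week t. A common slope therefore needs baseline to have the same covariance with all four follow-up scores. If the link with baseline weakens over time, the slope becomes steeper, and the week-4 difference is adjusted with a slope that is too shallow.

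What is at stake is precision at the one time point that decides the trial. Part of any chance baseline imbalance would stay in the week-4 contrast. Averaged over randomisations, that remainder appears as slightly more variance. These are two views of one effect, not two separate losses.

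**Working it through.** **Inputs from the documents.** SD of change 11 and target difference 4.2 on the 0-50 scale; "108 evaluable subjects per group, 5 % level of significance, two-sided" (SAP 2.2); four post-baseline visits; AR(1) covariance.

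**Assumed, because the documents give no values.** Baseline SD 5 to 8, AR(1) correlation rho 0.4 to 0.8, and the slope patterns below.

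**1. The plan's own figure.** SE = 11 × sqrt(2/108) = 1.497. Power = Φ(4.2/1.497 - 1.960) = Φ(0.846) = 0.80, as stated. The other cells of SAP Table 2 also reproduce, to within 0.01.

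**2. The slope applied at week 4.** With complete data, the week-4 estimate is the raw week-4 difference minus gbar times the baseline imbalance. Under AR(1), gbar weights the four visit slopes in proportion to 1, 1-rho, 1-rho, 1, with sum 4-2rho. The week-4 weight is 1/(4-2rho):
- rho 0.4: 1/3.2 = 0.31
- rho 0.8: 1/2.4 = 0.42

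So 58% to 69% of the slope comes from weeks 1 to 3. In each pattern below the weights are symmetric and the inner and outer pairs of slopes have the same mean, so gbar does not depend on rho.

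**3. Size at week 4.** With gap = g4 - gbar:
- one-SE imbalance = SD_X × sqrt(2/108) = 0.136 × SD_X
- residual = |gap| × imbalance
- excess variance = gap² × SD_X² / (week-4 residual variance)

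The residual variance is 121 - g4² × SD_X² in the first four rows. In the last two it is 100 (a residual SD of 10).

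| Slopes, weeks 1 to 4 | gbar | Gap | SD_X | Residual (points) | Excess variance |
|---|---|---|---|---|---|
| equal | same | 0 | any | 0 | 0 |
| -0.30, -0.35, -0.40, -0.45 | -0.375 | 0.075 | 5 to 8 | 0.05 to 0.08 | 0.1% to 0.3% |
| -0.20, -0.30, -0.40, -0.50 | -0.350 | 0.150 | 5 to 8 | 0.10 to 0.16 | 0.5% to 1.4% |
| -0.20, -0.35, -0.45, -0.60 | -0.400 | 0.200 | 5 to 8 | 0.14 to 0.22 | 0.9% to 2.6% |
| linear, -0.10 to -0.35 | -0.225 | 0.125 | 7.5 | 0.13 | 0.9% |
| linear, -0.05 to -0.50 | -0.275 | 0.225 | 7.5 | 0.23 | 2.8% |

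Example, last row: imbalance 7.5 × 0.136 = 1.02; residual 0.225 × 1.02 = 0.23; excess variance 0.225² × 56.25/100 = 2.8%.

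Where slopes differ, the residual is about 3% to 17% of the SE of the contrast (1.35 to 1.47). The gain in power from visit-specific slopes is under 1 percentage point in every row. Point values double on the 0-100 scale that the SAP uses for analysis; percentages do not change.

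**4. Check with dropout.** REML AR(1) simulation: three arms of 120, about 10% dropout at random given observed scores, rho 0.6, baseline SD 6.5, 800 replicates per pattern. The variance ratio, common over visit-specific slope, was 0.997 (equal slopes), 1.004 (-0.20 to -0.50) and 1.014 (-0.20 to -0.60). Mean estimates differed by less than 0.01 points and power by at most 0.2 percentage points.

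**The case against.** The case for leaving the model alone is that the loss depends on slopes the documents never show, that it is small even when they differ, and that a common slope contradicts nothing in the protocol or SAP. The steepest pattern above starts at -0.05, which means almost no regression to the mean at week 1 in subjects selected on a screening pain window. All of this stands, and it is why the point is minor. The SAP also holds sex, country and unilateral/bilateral status constant over visits. Baseline differs from these because it is subtracted to form the response, so a slope that changes with time is easier to expect.

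Three stronger readings are tempting, and the documents support none of them.

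- **A biased primary contrast.** A reader might infer this from an imperfect slope. Under randomisation the expected baseline imbalance is zero, so the estimate is unbiased on average and the type I error is not at risk. The residual exists only conditionally on a chance imbalance.
- **Harm from any dropout related to baseline pain.** In simulation, dropout driven by baseline equally in both arms moved the week-4 difference by less than 0.01 points. Shifts of roughly 0.1 to 0.3 points appeared only when the relation differed between arms (opposite directions). Nothing in the documents suggests that.
- **A larger loss of precision.** If correlation with baseline decays as phi^t, with phi 0.7 to 0.9 and a follow-up SD equal to a baseline SD of 7.5, the excess variance is 2.5% to 4.7%. But the week-4 SD of change is then 7.5 × sqrt(2(1 - phi⁴)), or 6.2 to 9.2, below the 11 on which the plan is powered.

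**Conclusion.** The point holds as a minor, free improvement. It is exact that one baseline slope is fitted and that most of it comes from visits other than week 4. The consequence is conditional. If slopes differ by visit, about 0.05 to 0.23 points on the 0-50 scale stay unadjusted per one-SE imbalance, and the week-4 variance is about 0.1% to 3% too large. If slopes are equal, the loss is zero. These sizes rest on assumed baseline SDs, slope patterns and correlations. The optional robustness work does not settle the matter, because it neither commits to this model nor names it. The validity of the primary test is not in question.

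**What to change.** In SAP 4.2.1.2, replace `baseline` by `baseline baseline*visit` in the sample code and add the baseline-by-timepoint interaction to the model text. Apply the same change to the models built on it in SAP 4.2.2.2 and 4.2.3.2, and make it before the blind is broken. The SAP already adds sex, country and unilateral/bilateral status to the protocol's model, so this fits the same pattern. The week-4 treatment contrast is requested and read as before.

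The cost is one degree of freedom per post-baseline visit beyond the first: 3 for WOMAC, PGA and ICOAP scores (four visits), 2 for WPAI (weeks 1, 2 and 4), and 1 for the chair-stand test (weeks 2 and 4) and EQ5D VAS (weeks 3 and 4). With about 108 evaluable subjects per arm this is negligible: with equal slopes, the simulated variance ratio was 0.997. If the sponsor prefers to keep the primary model unchanged, naming the extended model as a prespecified sensitivity analysis is the minimum.

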### 4.2.2 Secondary efficacy analyses

The secondary efficacy analyses will include data from the double-blind treatment groups only.

#### 4.2.2.1 Secondary endpoints

#### **WOMAC Osteoarthritis Index**

The WOMAC Osteoarthritis Index consists of 24 questions about aspects of the target knee over the previous 24 hours. The questions are split into three sections: *Pain, Stiffness* and *Difficulty Performing Daily Activities* (i.e. Physical Function). Each question is scored on a 0-10 11-point numerical scale, where higher numbers indicate greater pain, stiffness or difficulty in performing daily activities.

WOMAC scores	Range (min – max)	Derivation
Total score	0 - 240	Q1 + Q2 + + Q23 + Q24
Pain sub-score	0 - 50	Q1 + Q2 + Q3 + Q4 + Q5
Pain weight bearing sub-score	0 - 30	Q1 + Q2 + Q5
Pain non-weight bearing sub-score	0 - 20	Q3 + Q4
Stiffness sub-score	0 - 20	Q6 + Q7
Function sub-score	0 - 170	Q8 + Q9 + + Q23 + Q24

The following scores are derived from answers to the WOMAC questionnaire:

For convenience and ease of interpretation, all WOMAC derived scores will be normalised to a 0-100-point scale for data analysis where, for each score

#### normalised score = (score/max possible value) \* 100

The full WOMAC questionnaire is assessed for the target knee at baseline (Visit 2), week 1 (Visit 3) and weeks 2, 3 and 4.

The WOMAC pain sub-scale is also completed at screening for both the left/right hips and the left/right knees. This is for the assessment of baseline status and eligibility, the determination of the target knee and whether the subject has bilateral or unilateral knee OA.

#### Patient Global Assessment (PGA) questionnaire

The PGA consists of a single question asking how a patient's knee OA has affected their health during the last 48 hours. It is scored on an 11-point numerical rating scale from 0 to 10, where higher scores represent a higher level of disease activity or worse health.

The PGA is assessed at baseline and weeks 1, 2, 3 and 4.

#### Intermittent and Constant OA Pain (ICOAP)

The ICOAP consists of 11 items (questions) assessing pain in the target knee over the previous week. Each question is scored on a 5-point scale as follows, where higher scores indicate more severe pain:

- 0 = no pain
- 1 = mildly
- 2 = moderately
- 3 = severely
- 4 = extremely

The following scores are derived from answers to the ICOAP questionnaire:

ICOAP scores	Range	Derivation
Total	0 - 44	$Q1 + Q2 + \dots + Q10 + Q11$
Constant pain	0 - 20	Q1 + Q2 + Q3 + Q4 + Q5
Intermittent pain	0 - 24	Q6 + Q7 + Q8 + Q9 + Q10 + Q11

All ICOAP scores will be normalised to a score out of 100 using the formulae:

Normalized total pain score = (total pain score/44) \* 100

Normalized constant pain sub-score = (constant pain sub-score/20) \*100

Normalized intermittent pain sub-score = (intermittent pain sub-score/24) \*100

The ICOAP is assessed at baseline and weeks 1, 2, 3 and 4.

#### **Chair-stand test**

The chair-stand test is the number of times a subject can stand up and then sit down again in 30 seconds without using their arms. Higher numbers correspond to greater physical function.

The chair-stand test is performed at baseline, week 2 and week 4.

#### **Rescue Medication (paracetamol/acetaminophen)**

The total dose of rescue medication (g) taken will be determined as

total # of tablets of rescue medication used  $\times 0.5$ 

where,

total # of tablets used = (#of tablets used between V2 & V4) + (#of tablets used between V4 & V6)

and

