WOMAC Questionnaire 		X	X 	X	X	X	X	
ICOAP Questionnaire 			X	X	X	X	X	
Pain Diary 			X 	X 	X 	X 	X 	
Patient Global Assessment			X	X	X	X	X	
WPAI			X	X	X		X	
EQ5D			X			X	X	
Satisfaction questionnaire					X		X	
Chair-stand test 			X		X		X	
Selection of target knee			X					
Height and weight	X						X 	
Blood pressure and heart rate	X		X	X	X	X	X	

Protocol ID  
 AMZ001-006  
 Version 1.2

22NOV2018

Activity/Assessment	Screening 1a 	Screening 1b 	Baseline V2	On Treatment Visits				14-Day Safety Follow-up  V7
				V3	V4	V5	V6	
Study Week	-	-	0	1	2	3	4	6
Study Day	-21 to -5	-13 to -1	1	8	15	22	29	43
Adverse events	X 	X	X	X	X	X	X	X
Concomitant medication	X	X	X	X	X	X	X	X
Randomization			X					
Study drug dispensation and weighing of kit(s)			X		X 			
Dispensation of IMP "instructions for use" pamphlet			X		X			
Instruction of study drug application and frequency of use			X					
Application of morning study drug on site under staff supervision			X	X	X	X	X	
Weighing of kit(s) for compliance assessment				X	X	X	X	
Rescue medication dispense			X		(X) 	(X) 		
Rescue medication collection 					(X) 	(X) 	X	
12 lead ECG	X						X	
(Rescue) Analgesic Wash-out		X	X	X	X	X	X	
Hematology	X			X	X	X	X	
Safety chemistry and urine dipstick	X			X	X	X	X	
Pregnancy test 	X		X		X		X	
Blood sample for plasma level of diclofenac 					X		X	

EQ5D: EuroQol-5 Domain. ICOAP: Intermittent and Constant Osteoarthritis Pain. WOMAC: The Western Ontario and McMaster Universities Osteoarthritis Index. WPAI: Work Productivity Activity Index.

1. If subject is washed out of analgesics at Screening Visit 1a, the examinations scheduled for screening visits 1a and 1b can be performed on the same day.

Protocol ID  
AMZ001-006  
Version 1.2

22NOV2018

2. Phone call.
3. Skin assessment to be performed prior to application of study drug at baseline visit.
4. Subjects will be educated on appropriate expectations around their participation in a clinical study and the importance of reliably consistently and accurately reporting their pain throughout the study.
5. WOMAC pain sub-score (5 questions) to be assessed on a daily basis on paper at home during first week of treatment, i.e. the period between Visit 2 and Visit 3.

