6. Assessed without analgesic medication for five half-lives of the analgesic.
7. WOMAC assessment of hips should only be performed at the screening visit.
8. To be completed daily in the evening during the first week of treatment, i.e. between Visit 2 and Visit 3. In the period between other subsequent visits, the questionnaire will be completed during the evening of the day prior to the next visit.
9. Only weight collected.
10. Conditions previously unknown to the subject at the time of the screening visit will be recorded as medical history. All subsequent events will be recorded as adverse events.
11. To be collected/dispensed if previously dispensed supply of rescue medication was depleted and empty packaging returned to site.
12. Collection of remaining rescue medication at Visit 6. Empty packaging of previously dispensed kit should be returned to the site if new rescue medication is requested.
13. Serum test at screening visit, urine dipstick at all other visits.
14. To be done after IMP application and questionnaire/test completion (approximately 1-2 hours after IMP application). Exact time of IMP application and time of blood sampling must be documented.
15. Dispensation is not mandatory for subjects allocated to Voltaren® gel

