#### 1.1.2 Endpoints

The primary endpoint of this study (double-blind treatment groups only) is:

• The change from baseline in WOMAC pain sub-score (questions 1 to 5) in the target knee as evaluated at week 4.

The secondary endpoints of this study (double-blind treatment groups only) are:

- Changes from baseline in WOMAC total score and the WOMAC function and stiffness scores at week 4
- Changes from baseline in constant and intermittent OA pain assessed by ICOAP scores at week 4
- Changes from baseline in WOMAC pain weight-bearing score (questions 1, 2, and 5) and non-weight bearing score (questions 3 and 4) at week 4
- Changes from baseline in physical function assessed by the chair-stand test at week 4
- OMERACT-OARSI responder rate at week 4
- Total dose of rescue medication calculated as the sum of tablets used, based on pill counts
- Time between baseline and first use of rescue medication
- Changes from baseline in WOMAC pain sub-score (questions 1 to 5) between groups receiving AMZ001 QD and BID in the target knee as evaluated at week 4

- Changes from baseline in constant and intermittent OA pain assessed by ICOAP scores between groups receiving AMZ001 QD and BID at week 4
- Changes from baseline in WOMAC pain weight-bearing score (questions 1, 2, and 5) and non-weight bearing score (questions 3 and 4) between groups receiving AMZ001 QD and BID at week 4
- Changes from baseline in physical function assessed by the chair-stand test between AMZ001 QD and BID at week 4
- Changes from baseline in WOMAC total score and the WOMAC function and stiffness scores between AMZ001 QD and BID at week 4.
- Changes from baseline in the impact of OA on daily living as assessed by the PGA score at week 4
- Changes from baseline in work productivity and activity assessed by the WPAI at week 4
- Changes from baseline in quality of life assessed by the EQ5D at week 4

The safety endpoints of this study are:

- Nature, incidence and severity of AEs
- Changes in laboratory safety parameters, vital signs, 12-lead ECG parameters and weight
- Nature, incidence and severity of skin reactions on the application site

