- 1. If subject is washed out of analgesics at Screening Visit 1a, the examinations scheduled for screening visits 1a and 1b can be performed on the same day.
- 2. Phone call.
- 3. Skin assessment to be performed prior to application of study drug at baseline visit.
- 4. Subjects will be educated on appropriate expectations around their participation in a clinical study and the importance of reliably consistently and accurately reporting their pain throughout the study.
- 5. WOMAC pain sub-score (5 questions) to be assessed on a daily basis on paper at home during first week of treatment, i.e. the period between Visit 2 and Visit 3.
- 6. Assessed without analgesic medication for five half-lives of the analgesic.
- 7. WOMAC assessment of hips should only be performed at the screening visit.

- 8. To be completed daily in the evening during the first week of treatment, i.e. between Visit 2 and Visit 3). In the period between other subsequent visits, the questionnaire will be completed during the evening of the day prior to the next visit.
- 9. Only weight collected.
- 10. Conditions previously unknown to the subject at the time of the screening visit will be recorded as medical history. All subsequent events will be recorded as adverse events.
- 11. To be collected/dispensed if previously dispensed supply of rescue medication was depleted and empty packaging returned to site.
- 12. Collection of remaining rescue medication at Visit 6. Empty packaging of previously dispensed kit should be returned to the site if new rescue medication is requested.
- 13. Serum test at screening visit, urine dipstick at all other visits.
- 14. To be done after IMP application and questionnaire/test completion (approximately 1-2 hours after IMP application). Exact time of IMP application and time of blood sampling must be documented.
- 15. Dispensation is not mandatory for subjects allocated to Voltaren® gel

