# of tablets used between Vi and Vj = (# tablets dispensed at Vi) - (# tablets returned at Vj) - (# tablets unaccounted for at Vj)

The average dose of rescue medication per day while on study drug (g/day) will be determined as

total dose of rescue medication used (g) number of days on study drug

where,

 $number of days on study drug = \{ \begin{array}{ll} duration of exposure, \\ duration of exposure - 1, \end{array} if trt end date < V6 account date \\ if trt end date = V6 account date \\ \end{array} \}$ 

Note: a consistent approach to determining 'number of days on study drug' is taken across exposure, compliance and rescue medication calculations.

The time between baseline and first intake of rescue medication (days) will also be determined as

Date of first intake of rescue medication - treatment start date

For subjects that have first intake of rescue medication on the Visit 2 (treatment start) date, the time to first intake of rescue medication will be set to 0.5 days.

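### The SAP's rescue-tablet formula has no term for tablets dispensed at Visit 5, so every subject re-supplied there is under-counted by one supply

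*SAP*

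**What the plan says.** SAP section 1.1.2 lists among the secondary endpoints "Total dose of rescue medication calculated as the sum of tablets used, based on pill counts". Section 4.2.2.1, under Rescue Medication, builds the total from two intervals: "total # of tablets used = (#of tablets used between V2 & V4) + (#of tablets used between V4 & V6"). For an interval running from Vi to Vj, the count is the "tablets dispensed at Vi) - (# tablets returned at Vj"), less tablets unaccounted for at Vj. Tablets are multiplied by 0.5 to give grams, and the total is divided by days on study drug to give g/day. Section 4.2.2.2 analyses g/day by ANCOVA, with treatment differences, confidence intervals and p-values.

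The schedules (protocol Table 2; SAP section 2.1, Table 1) show when tablets change hands. The row "Rescue medication dispense" is marked at V2 and, conditionally, at both V4 and V5. Footnote 11 gives the condition: "To be collected/dispensed if previously dispensed supply of rescue medication was depleted and empty packaging returned to site". Footnote 12 provides for "Collection of remaining rescue medication at Visit 6" and adds: "Empty packaging of previously dispensed kit should be returned to the site if new rescue medication is requested".

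**The concern.** The formula knows two dispensing visits, V2 and V4, while the schedule has three. A supply handed out at V5 falls inside the V4 to V6 interval but not at its opening visit, so it is not counted as dispensed. Its leftovers are still counted as returned at V6.

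The error is not random. Re-supply at V5 requires an exhausted earlier supply, so the tablets removed belong to the heavier users. If V5 re-supply is more frequent on placebo than on active gel, the difference in rescue use shrinks; if the imbalance runs the other way, the difference is distorted in the other direction. The quality control in SAP section 5 would not necessarily reveal this: two programmers who independently follow the same formula will agree on the same wrong total.

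**Working it through.** **Notation.** D, R and U are tablets dispensed, returned and unaccounted for; the number is the visit. S is the size of one supply, taken as equal at each dispensing (assumption; not stated in the documents). Tablet strength is 500 mg (protocol synopsis, Rescue medication).

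**SAP formula expanded:** F = (D2 − R4 − U4) + (D4 − R6 − U6).

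**Full accounting:** T = (D2 + D4 + D5) − (R4 + R5 + R6) − (U4 + U5 + U6).

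**Difference:** T − F = D5 − R5 − U5. Under footnote 11, a subject re-supplied at V5 has used up the earlier supply and brings back empty packaging, so R5 = 0. If unaccounted tablets are captured at V4 and V6, as the formula provides, U5 = 0 as well, and the shortfall is D5, one supply.

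**Numerical check** with S = 50, R6 = 40, no other returns and nothing unaccounted for:

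| Re-supply | F | T | Shortfall |
|---|---|---|---|
| None | 50 − 40 = 10 | 10 | 0 |
| V4 only | 50 + 50 − 40 = 60 | 60 | 0 |
| V5 only | 50 − 40 = 10 | 100 − 40 = 60 | 50 |
| V4 and V5 | 100 − 40 = 60 | 150 − 40 = 110 | 50 |

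Enumerating every R6 from 0 to S, for S = 10, 20, 50 and 100, gives the same pattern: a shortfall of S whenever there is V5 re-supply, and 0 otherwise.

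**Recorded use as a share of true use**, where k is the fraction of the V5 supply consumed (assumed 0.2, 0.5, 0.8):

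- V5 only: kS / (S + kS) = k/(1 + k) = 17%, 33%, 44%.
- V4 and V5: (S + kS) / (2S + kS) = (1 + k)/(2 + k) = 55%, 60%, 64%.

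**Loss per affected subject** for assumed S = 20, 50, 100: 0.5 × S = 10, 25, 50 g. Over a nominal 28 days, 0.5 × S/28 = 0.36, 0.89, 1.79 g/day.

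**Loss in an arm mean** = share of the arm re-supplied at V5 × loss per subject. At an assumed 10%: 0.04, 0.09, 0.18 g/day.

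**Edge case.** A subject who finishes the V2 supply, is re-supplied only at V5 and returns that supply intact has F = S − S = 0, although S tablets were taken.

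**The case against.** Nothing in either document supplies the missing term; the objections concern precision and size.

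- *The shortfall may not be exactly one supply.* If tablets are logged as unaccounted for at V5 and not carried to V6, it is D5 − U5: with S = 20 and U5 = 2, 5 or 10, it is 18, 15 or 10 tablets. If returns were matched kit by kit, it would be the tablets used from the V5 kit, between 0 and S. A programmer might also read the dispensing term as covering the whole interval. These are fair qualifications, but each departs from the formula as written or from how it handles unaccounted tablets.
- *The largest supply does not fit every scenario.* The protocol caps rescue at 4 g/day, or 8 tablets. From V4 to V5 is nominally 7 days (56 tablets), and at most 11 days with the visit windows (88 tablets). Within the cap, a 100-tablet supply cannot be exhausted between V4 and V5, so that figure applies only to V5-only re-supply, which needs 100 × 0.5/21 = 2.4 g/day over the first 21 days. This stands.
- *A fixed 10% share is generous for large supplies.* For a given level of use, fewer subjects exhaust a larger supply, so 0.18 g/day probably overstates the top of the range. If supplies are large, V5 re-supply may be rare or absent. This stands too.
- *The reach is limited.* This is one secondary endpoint among many. Time to first use is date-based ("Date of first intake of rescue medication - treatment start date") and unaffected. The count of subjects with any rescue use is exposed only in the edge case, and only if it is taken from pill counts. SAP section 4.2.2.2 assigns non-users a zero dose, which suggests they are identified separately, but the SAP does not state the source.

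**Conclusion.** The formula is wrong as written and should be corrected. It contradicts the SAP's own schedule and gives a wrong total dose and g/day for each subject re-supplied at V5. The shortfall is the supply dispensed at V5, provided that footnote 11 is followed and unaccounted tablets are captured at V4 and V6. Its size in grams, and its effect on the treatment comparison, cannot be fixed from the documents, because supply size and V5 re-supply frequency are not given; the gram and g/day figures above are illustrations under stated assumptions. The primary analysis is not affected.

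**What to change.** Before unblinding, replace the two-interval sum in SAP section 4.2.2.1 with a single account: total tablets used = (dispensed at V2 + V4 + V5) − (returned at V4 + V5 + V6) − (unaccounted for at V4 + V5 + V6), with each unaccounted tablet entered once. Derive total dose and g/day from this total. State whether the any-use count comes from it or from the recorded date of first intake.

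The cost is one SAP formula and its derivation program. Dispensing and collection at V5 are already scheduled in both documents, so no new procedure is needed, and subjects not re-supplied at V5 keep the same total.
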